HIV viral resistance to antiretrovirals (ARV), whether transmitted or acquired following long-term antiretroviral therapy (ART) exposure, can greatly limit therapeutic options.^[1-8] As a result, a subset of people with HIV (PWH) referred to as heavily treatment-experienced (HTE) require highly tailored ART regimens with less common ARV combinations.^[9] In the US, HTE prevalence has been estimated to range from 2% to 14% in 2016-2017.^[10, 11] The prognosis for HTE PWH may be less favorable compared to less experienced PWH. Notably, multidrug resistance (MDR) has been associated with a higher risk of death, AIDS-defining events (ADE) and viral rebounds.^[9, 12-14] Though the development of new ARVs has increased the number of treatment options available, there are still individuals who cannot achieve complete virologic suppression and remain at risk for disease progression.^[15]

The US Department of Health and Human Services (DHHS) HIV treatment guideline suggest that IBA may be considered in the context of MDR without fully active ART options, namely among PWH with ongoing detectable viremia and lacking sufficient options to build a fully suppressive regimen.^[16] However, clinical trials assessing IBA efficacy did not include an active comparison arm in which participants did not receive IBA. An external comparison analysis has been conducted between IBA + optimized background regimen (OBR) from clinical trials (TMB-202, TMB-301/311), and non-IBA OBR from a European registry. The OPERA study will improve upon this European registry study with a larger sample size and the use of controls from the same geographic region as the trial participants.

It is important to assess the comparative effectiveness of IBA compared to other regimens used in the routine clinical care of HTE PWH with MDR HIV. The use of external controls can provide valuable information and context to interpret the results of clinical trials when randomization to a control arm cannot be performed.^[17] Using comparable populations and larger sample sizes may reduce bias and improve the power of analyses. The OPERA (Observational Pharmaco-Epidemiology Research & Analysis) cohort, a large US electronic health record (EHR) database, is well suited for this as the OPERA and trials populations arose from the same geographic location (i.e., US), and the number of OPERA PWH potentially meeting inclusion criteria is high. Therefore, an external comparison of IBA+OBR from trials to non-IBA OBR in routine clinical care in the OPERA cohort may confirm results from prior studies suggesting viral control benefits of IBA+OBR.

Study Objectives

Primary Objective:

To assess the virologic effectiveness of 800 mg IBA every 2 weeks + OBR (TMB-202 & TMB-301/311 trials), compared to non-IBA OBR in routine clinical care (OPERA cohort), among HTE PWH.

Sensitivity Objective 1:

To assess the robustness of results from the primary objective to the viremia threshold for inclusion in the OPERA non-IBA OBR group (main: VL >1,000 copies/mL vs. sensitivity: VL >200 copies/mL).

Sensitivity Objective 2:

To replicate previous analyses of the European registry as closely as possible, taking into consideration the differences between the registry and OPERA datasets

Data sources

Data from the phase 2 clinical trial TMB-202, as well as the phase 3 trial TMB-301 and its extension TMB-311 will be used for the treatment arm of the study (IBA+OBR). The OPERA cohort, which includes complete EHR data from over 143,000 PWH across 142 separate locations throughout the US, will be used for the control arm (non-IBA OBR).

Study Design

All TMB-202 and TMB-301/311 trial participants randomized to 800 mg IBA every 2 weeks with or without a loading dose will be included in the main analyses. From the OPERA cohort, adult PWH with resistance from three ARV classes will be considered for inclusion (see section 3.2.1 for more details). OPERA PWH initiating a new non-IBA OBR between 01JAN2008 and 31DEC2020 will be included; person-time will be censored at the first of (a) initiation of a select potent ARV, (b) >45 days without ART, (c) 12 months after last clinical contact, (d) death, or (e) study end (i.e., extract date of the dataset; TBD). Viral suppression (i.e., <200 copies/mL) and undetectable viral load (i.e., <50 copies/ml) will be assessed at each of the timepoints of interest (i.e., weeks 24, 48, 60 and 96), using the closest measurement to the timepoint within a ± 6 -week window.

Statistical Analyses

Multiple imputation will be used to ensure that eligible OPERA participants can contribute to all timepoint analyses even if their routine clinical care resulted in viral loads being measured outside of the ranges defined in the protocol. To prevent the introduction of a bias towards the null, imputation will be performed in the OPERA non-IBA OBR group separately.^[18] 95% confidence intervals will be obtained through bootstrapping.

First, the data will be sampled with replacement to create 500 bootstrap samples. Within each bootstrap sample, multiple imputation will be implemented using chained equations, producing 10 imputed datasets per bootstrap sample.

Within each imputed dataset, analyses will be performed to obtain an estimate at each timepoint for all 5,000 datasets (i.e., 500 bootstrap samples * 10 imputed datasets). Risk ratios for both viral suppression and undetectability will be estimated as a measure of comparative virologic effectiveness of IBA+OBR vs. non-IBA OBR at each timepoint. The *average treatment effect in the treated* (ATT) will be estimated using standardized mortality ratio (SMR)-weighting, a form of propensity score (PS)-weighting. SMR-weighting ensures that the distribution of baseline characteristics is the same in the control population as in the treated population.^[20] In other words, the external control population will be weighted to look like the treated population. Logistic regression will be used to obtain the PS and will include baseline values for important predictors of regimen selection. SMR weights are set to 1 in the treated population (i.e., TMB trials IBA+OBR) and to PS/(1-PS) in the control population (i.e., OPERA non-IBA OBR).^[20] The final set of variables included in the PS model will be determined by the distribution of weights, as well as the balance of covariates across groups before and after applying SMR weights.

Estimates of risk will be derived from SMR-weighted Kaplan-Meier curves. The cumulative probability of viral suppression or undetectability will be estimated at each timepoint of interest for each arm, from which risk ratios will be calculated. Estimates will be averaged across all datasets to obtain the combined estimate and 95% confidence intervals will be derived from the distribution of all estimates, using the 2.5th & 97.5th percentiles.

These analyses will be repeated for sensitivity objective 1 after restricting the OPERA non-IBA OBR group to PWH with a VL >1,000 copies/mL. For sensitivity objective 2, analyses performed using the European registry data will be replicated as closely as possible, taking into consideration the differences in design between the registry and OPERA datasets.

1. Background and Rationale

In 2020, over 37 million people were living with HIV infection worldwide, and 680,000 people died from AIDS.^[21] In regions of the world like the US with access to antiretroviral therapy (ART), the development of antiretrovirals (ARV) has prolonged life expectancy for people with HIV (PWH).^[22] However, long-term exposure to ART can eventually lead to fewer therapeutic options in multiple ARV classes.^[1, 2] This can be attributed to multiple factors including poor tolerability, drug toxicity, avoidance of drug-drug interactions, and viral resistance.^[2-6] As a result, a subset of PWH require highly tailored ART regimens with less common ARV combinations; these individuals are often referred to as heavily treatment-experienced (HTE).^[9] Moreover, while transmitted resistance has decreased over calendar time, it remains a concern among ART-naïve PWH; some ART-naïve individuals may thus also have limited treatment options.^[7, 8]

HTE prevalence varies depending on the setting and the definition used. In the US, HTE prevalence has been estimated to range from 2% to 14% in 2016-2017.^[10, 11] In Europe, HTE prevalence increased from 6% in 2010 to 9% in 2016; important geographic variation has also been observed, from 1% in Eastern Europe to 16% in Western/Central Europe.^[23]

The prognosis for HTE PWH appears to be less favorable compared to less experienced PWH. Increased risk of death and AIDS-defining events (ADE) have been reported among PWH with multidrug resistance (MDR).^[9, 12, 13] Moreover, triple ARV class failure has been associated with a higher rate of viral rebound (i.e., two consecutive viral loads > 400 copies/mL or one viral load > 400 copies/mL followed by initiation of at least 2 new ARVs).^[14] Published evidence suggests that mortality in people with HIV is associated with incomplete viral suppression. Studies investigating the effect of detectable HIV RNA after antiretroviral therapy and mortality rates in people with HIV identified that incomplete suppression of HIV RNA after receiving ART is associated with significant 10-year all-cause mortality risk.^[24, 25]

Complex ART regimens, which are characteristic of treatments for HTE PWH, may both lack sufficient efficacy and have adverse safety and tolerability profiles, making disease and toxicity management even more difficult.^[15, 26, 27] Though the development of new ARVs has increased the number of treatment options available for HTE PWH, there are still individuals who cannot achieve complete virologic suppression and remain at risk for disease progression.^[15] The US Department of Health and Human Services (DHHS) HIV treatment guideline suggest that ibalizumab (IBA) may be considered in the context of MDR without fully active ART options, namely among PWH with ongoing detectable viremia and lacking sufficient options to build a fully suppressive regimen.^[16]

The TMB-202 trial was a phase 2b study conducted between 2008-2010 in the US and Taiwan, in which 113 patients were randomized to receive either 800mg IBA every two weeks (n=59) or 2000mg IBA every four weeks (n=54), in addition to an optimized background regimen (OBR).^[28] The TMB-301 trial and its extension TMB-311 were phase 3 single arm studies of 40 patients (34 in the US, 4 in Taiwan, 2 in Puerto Rico). All received a loading dose of 2000mg IBA with their failing regimen, followed by 800mg IBA every two

weeks with an OBR.^[29] These trials did not include a comparison arm in which participants did not receive IBA. Indeed, given that the trials were restricted to failing individuals (i.e., viral load >1,000 copies/mL) with limited susceptibility to other approved ARVs, withholding IBA from some trial participants was deemed unethical. It is therefore important to assess the comparative effectiveness of IBA compared to other regimens used in routine clinical care of people with MDR HIV.

Such an external comparison analysis has been conducted against a European Registry, an observational, prospective, multi-center study. The OPERA study will improve upon this European registry study with a larger sample size and the use of controls from the same geographic region as the trial participants.

The use of external controls can provide valuable information and context to interpret the results of clinical trials when randomization to a control arm cannot be performed.^[17] However, careful consideration must be given to biases that may be introduced in such analyses. Regional bias, in which patient outcomes differ based on the geographic region due to differences in standard of care or demographic characteristics, can be reduced by selecting external controls in the same region where the trial was conducted.^[17] The Observational Pharmaco-Epidemiology Research & Analysis (OPERA) cohort is a large observational database electronic health record (EHR) from over 143,000 PWH across the US.

It is important to assess the comparative effectiveness of IBA compared to other regimens used in the routine clinical care of HTE PWH with MDR HIV. External comparisons of trial participants and PWH in routine clinical care may help assess the comparative effectiveness of IBA+OBR. Using a comparable external control and larger sample sizes may reduce bias and improve the power of such indirect comparisons. Therefore, an external comparison of IBA+OBR from the TMB-202 and TMB-301/311 trials and non-IBA OBR in routine clinical care in the OPERA cohort may confirm results from prior studies suggesting viral control benefits of IBA+OBR.

2. Study Objectives

Primary Objective

- I. To assess the virologic effectiveness of 800mg IBA every 2 weeks + OBR (TMB-202 & TMB-301/311 trials), compared to other ART regimens in routine clinical care (OPERA cohort), among HTE PWH.
 - External comparison (IBA+OBR in clinical trials vs. non-IBA OBR in OPERA)
 - Timepoint analysis
 - Multiple imputation of missing viral loads in OPERA
 - PS standardized mortality ratio-weighting

Sensitivity Objectives

- I. To assess the robustness of results from the primary objective to the viremia threshold for inclusion in the OPERA non-IBA OBR group (main: VL >1,000 copies/mL vs. sensitivity: VL >200 copies/mL).
- II. To replicate previous analyses of the European registry as closely as possible, taking into consideration the differences in design between the registry and OPERA datasets
 - External comparison (IBA+OBR in clinical trials vs. non-IBA OBR in OPERA)
 - Timepoint analysis
 - Complete case analysis
 - Propensity score matching (PS including baseline VL, CD4 cell count, number of potent ARVs scaled by the level of resistance, and the calendar period score)

3. Study Design

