2. Any significant diseases (other than HIV-1 infection) or clinically significant findings, including psychiatric and behavioral problems, determined from screening, medical history and/or physical examination that, in the investigator's opinion, would preclude the patient from participating in this study
3. Any acute illness within 1 week before the initial administration of study drug
4. Any active infection secondary to HIV requiring acute therapy; however, patients that require maintenance therapy (i.e., secondary prophylaxis for opportunistic infections) will be eligible for the study.
5. Any immunomodulating therapy (including interferon), systemic steroids, or systemic chemotherapy within 12 weeks before randomization
6. Any investigational therapy within 30 days before randomization, except for those HIV-agents available in expanded-access programs
7. Any prior exposure to ibalizumab (formerly TNX-355 and Hu5A8)
8. Any vaccination within 21 days before randomization
9. Any female patient who either is pregnant, intends to become pregnant, or is currently breastfeeding

TMB-301/TMB-311 trials

The TMB-301/311 trials (NCT02475629, NCT02707861)^[29, 32] were phase 3, single arm, multi-center studies of IBA+OBR in ART-experienced patients infected with MDR HIV-1. TMB-301 was a 24-week study and TMB-311 extended its follow-up to up to 96 weeks. All participants received 2000mg IBA IV (loading dose) as they maintained their current regimen, followed 14 days later by 800mg IBA IV every two weeks + OBR. A total of 40 patients were enrolled in TMB-301 (34 in the US, 4 in Taiwan, 2 in Puerto Rico), of which 27 US patients were enrolled into the extension study TMB-311 and continued to receive IBA+OBR at the dosage assigned in TMB-301. There were four deaths during the 24-week period of TMB-301, and two deaths during the TMB-311 period.

Inclusion Criteria (criteria applicable to OPERA are underlined)

1. Are capable of understanding and have voluntarily signed the informed consent document
2. Have documented HIV-1 infection
3. Have no AIDS-defining events in the 3 months before Screening, other than cutaneous Kaposi's sarcoma or wasting syndrome due to HIV
4. Are able and willing to comply with all protocol requirements and procedures
5. Are 18 years of age or older
6. Have a life expectancy that is >6 months

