3.2.2. Study Timelines

Study timelines are mapped out for the two trials and for OPERA in [Table 1](#).

TMB-202

- Recruitment: 2008-2010
- Follow-up: through week 24
- Index: date of first IBA infusion

TMB-301/311

- Recruitment: 2015-2018
- Follow-up: through week 96
- Index: date of first IBA infusion

⁴ CAB had not yet been approved at the time and is not indicating for ART-experienced PWH who are failing their current regimen

OPERA

- Identification of study participants: 01JAN2008 to 31DEC2020
- Censoring criteria:
 - Initiation of any of the following ARVs:
 - INSTI
 - PI
 - Fusion inhibitor (FI)
 - Gp120 inhibitor
 - IBA
 - Doravirine
 - Blinded ARV
 - >45 days without ART
 - 12 months after last clinical contact (i.e., telephone contact, visit, lab test, or consultation)
 - Death
 - Study end (i.e., extract date; TBD)
- Index: date of regimen initiation

Table 1. Alignment of study timelines for the clinical trials and OPERA

	Week -1	Index	Week 1	Week 24	Week 48	Week 60	Week 96
TMB-202	Failing Regimen	IBA 2000mg every 4 weeks + OBR ^a					
		IBA 800mg every 2 weeks + OBR ^a					
TMB-301/311	Failing Regimen	IBA 2000mg + Failing Regimen		IBA 800mg every 2 weeks + OBR ^a			
OPERA	Failing Regimen	Index regimen ^b					

^a Changes in OBR were allowed during follow-up

^b Some changes in ARVs will be allowed to be consistent with trial designs; person-time will be censored at initiation of an INSTI, PI, fusion inhibitor, Gp120 inhibitor, IBA, doravirine or a blinded ARV

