4.4. Primary Objective: External Comparison of Virologic Effectiveness

The comparative virologic effectiveness of IBA+OBR vs. non-IBA OBR will be assessed at each timepoint for both viral suppression (VL < 200 copies/ml) and undetectability (VL < 50

copies/ml). Within each imputed dataset, estimates of risk will be derived from SMR-weighted Kaplan-Meier curves. The cumulative probability of viral suppression or undetectability will be estimated at each timepoint of interest for each arm, from which risk ratios will be calculated.

The distribution of estimates from all 5,000 datasets will be used to obtain the final estimate (mean) and 95% confidence intervals (2.5th and 97.5th percentiles).

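### OPERA deaths are censored in a Kaplan-Meier estimate of suppression, and no rule is given for deaths in the trial arm

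*Combined protocol and SAP*

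**What the plan says.** The opening summary, under Study Design, sets the censoring rule for the controls: "OPERA PWH initiating a new non-IBA OBR between 01JAN2008 and 31DEC2020 will be included; person-time will be censored at the first of" five events, of which the last three are "c) 12 months after last clinical contact, (d) death, or (e) study end". Section 3.2.2 repeats the list under its OPERA heading, with death next to "12 months after last clinical contact (i.e., telephone contact, visit, lab test, or consultation". The TMB-202 and TMB-301/311 headings in that section give only recruitment, follow-up and index date. They contain no censoring criteria and no mention of death.

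Section 4.4 names the estimator: "estimates of risk will be derived from SMR-weighted Kaplan-Meier curves". It applies to both groups: "The cumulative probability of viral suppression or undetectability will be estimated at each timepoint of interest for each arm", and the risk ratio is formed from those two probabilities.

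Section 3.1.2 reports trial mortality: "There were four deaths during the 24-week period of TMB-301, and two deaths during the TMB-311 period". The denominator is also there: "A total of 40 patients were enrolled in TMB-301". No deaths are given for TMB-202 or OPERA, and the virologic status of the six who died is not given.

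No section treats death as a competing event or as failure to suppress. The two sensitivity analyses in Section 4.5 concern the viral load threshold and the registry replication. Section 4.2 imputes missing OPERA viral loads with no stated exception for timepoints after death. Section 3.2.1, item 15, admits OPERA patients only if they have a viral load after index; the trial group has no such condition.

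**The concern.** The event being counted is favourable, and death before it rules it out for good. Kaplan-Meier treats a censored person as someone who would have gone on to suppress at the same rate as those still under observation. That is a reasonable assumption for administrative censoring at the data cut, but it cannot be true of a person who has died. One minus Kaplan-Meier therefore exceeds the share of the group that actually suppressed whenever anyone dies unsuppressed.

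Two things are at stake. First, the reported risk is no longer a proportion of the arm. Second, the comparison depends on a choice the plan leaves open. Control deaths are censored, while trial deaths could be censored, kept as non-suppressed, or handled in some other way. An analyst who fills that gap after seeing the data can move the risk ratio. Section 4.3 sets out to mimic a hypothetical randomised trial, and that calls for the same death rule in both arms.

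**Working it through.** **Inputs from the documents.** Treated group: 59 (TMB-202) + 40 (TMB-301/311) = 99, which reproduces the figure in Section 5. Deaths (Section 3.1.2): 4 by week 24 + 2 in the extension = 6. Shares: 6/40 = 15.0% of TMB-301/311; 4/99 = 4.0% and 6/99 = 6.1% of the pooled arm, TMB-202 deaths being unknown.

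**Assumptions.** All reported trial deaths were unsuppressed. True suppression is 30% to 70%. The share of OPERA patients dying unsuppressed is 0% to 15%. The documents give none of these.

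**Step 1: ceiling on the treated arm if its deaths were censored.** The overstatement is largest when every death precedes every suppression, and is then n/(n − d).
- Week 24: 99/95 = 1.04.
- All six deaths: 99/93 = 1.06. This treats all 99 as followed beyond week 24. TMB-202 follow-up ends at week 24, so its diluting effect weakens later and the figure is only a guide there.

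**Step 2: a less extreme pattern.** With constant competing hazards, p the true cumulative incidence of suppression and d the share dying unsuppressed,

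Kaplan-Meier probability = 1 − (1 − p − d)^(p/(p + d)).

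For p from 30% to 70%, the overstatement is 0.7 to 2.1 percentage points with d = 4/99, and 1.1 to 3.2 points with d = 6/99.

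**Step 3: effect on the risk ratio.** Take p = 50% in both arms (true ratio 1.00) and d = 6/99 in the treated arm. If treated deaths are censored, the treated estimate is 1 − 0.4394^0.892 = 0.520. For controls with d = 15%, it is 1 − 0.35^0.769 = 0.554. The ratio is 0.520/0.554 = 0.94. If trial deaths instead count as not suppressed, the treated estimate stays at 0.50 and the ratio is 0.50/0.554 = 0.90.

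| OPERA share dying unsuppressed | Ratio, deaths censored in both arms | Ratio, OPERA deaths censored and trial deaths counted as not suppressed |
|---|---|---|
| 0% | 1.04 | 1.00 |
| 6.1% | 1.00 | 0.96 |
| 10% | 0.97 | 0.94 |
| 15% | 0.94 | 0.90 |

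With equal shares and equal suppression the bias cancels. With equal shares and suppression of 50% against 40%, the true 1.25 is estimated as 1.253, so the cancellation is nearly complete.

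**Step 4: does reading the outcome as status at each timepoint avoid this?** The Study Design summary and Section 3.3.2 define the outcome by the viral load nearest each timepoint, whereas Section 4.4 uses a cumulative curve. Under the status reading, an OPERA patient who has died is either dropped from the denominator or given an imputed viral load. Both still treat that person as possibly suppressed.

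**The case against.** The strongest reply is that the written rule and the reported deaths belong to different arms. The censoring list is for OPERA, while the six deaths are in the ibalizumab trials. A reader might infer that the plan censors those six people and so flatters ibalizumab. The documents do not support that, because they give no rule for trial deaths. The one rule they do state raises the control probability and works against ibalizumab. This part of the objection stands.

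A reader might also divide 40 by 34 and report an 18% overstatement. That figure describes no planned analysis, since the treated arm is pooled. It also requires that nobody suppressed before any of the six deaths, two of which fell in the extension period, and it ignores that only 27 of the 40 entered the extension.

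The size is modest. At 50% suppression, the 95% sampling margin for 99 people is 1.96 × √(0.25/99) = 9.8 points, against a constant-hazards overstatement of 0.7 to 2.1 points at week 24. The bias also cancels if the arms have similar shares of unsuppressed deaths.

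Finally, Section 1 links incomplete suppression to mortality, but partly over ten years and not in these patients. Anyone who suppressed before dying has already been counted as an event and causes no bias in the cumulative curve. So it is an assumption that the six died unsuppressed.

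These points limit the size and leave the net direction open. They do not rescue the rule: censoring at death is the wrong treatment of a terminal event here, and the trial arm still has no rule.

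**Conclusion.** The concern holds in a limited form. Followed as written, the plan overstates suppression among OPERA controls if any of them die unsuppressed, which lowers the risk ratio. It leaves trial deaths undefined although 6 of 40 TMB-301/311 participants died. It does not show a bias in favour of ibalizumab: that would need trial deaths to be censored as well, and a larger share dying unsuppressed in the trial arm than in OPERA.

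The likely effect on the ratio is a few percent. It reaches about 6% downward if both arms are censored, and about 10% downward if only controls are, when 15% of OPERA patients die unsuppressed. These figures rest on assumed suppression levels, assumed OPERA mortality, constant hazards, no TMB-202 deaths and the six trial deaths all being unsuppressed. The matter should be settled before analysis because the correction is standard and cheap and the open choice can move the primary estimate.

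**What to change.** - Take death off the censoring list in the Study Design summary and Section 3.2.2, and write one rule for both arms. If the cumulative curve in Section 4.4 is kept, use SMR-weighted cumulative incidence with death before suppression as a competing event. If status at each timepoint is meant, classify anyone dead by that timepoint as not suppressed.
- State in Section 4.2 that viral loads are not imputed after death.
- Deal with Section 3.2.1, item 15. It removes OPERA patients who died before any follow-up viral load but leaves early trial deaths in, so a common death rule alone would count early deaths in one arm only. Either drop the requirement and rely on the planned imputation, or report how many OPERA patients who died it excludes and add a sensitivity analysis that includes them.
- Report deaths by arm and timepoint, including any in TMB-202.

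The cost is some SAP wording and a standard weighted cumulative-incidence routine inside the existing bootstrap. Suppression figures will be slightly lower, and the control arm will depend on how completely the electronic records capture deaths.
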